### 8.3.2 Serious Adverse Event

An adverse event is considered "serious" if, in the view of the investigator, it results in any of the following outcomes:

- Death  
If death results from (progression of) the disease, the disease should be reported as event (SAE) itself.
- A life-threatening adverse event  
An adverse event is considered 'life-threatening' if, in the view of either the investigator, its occurrence places the patient or subject at immediate risk of death. It does not include an adverse event that, had it occurred in a more severe form, might have caused death.
- Inpatient hospitalization or prolongation of existing hospitalization for  $\geq 24$  hours.
- A persistent or significant incapacity or substantial disruption of the ability to conduct normal life functions

- A congenital anomaly/birth defect

- Important medical event

Any event that may not result in death, be life-threatening, or require hospitalization may be considered serious when, based upon appropriate medical judgment, they may jeopardize the patient and may require medical or surgical intervention to prevent one of the outcomes listed in this definition of "Serious Adverse Event". Examples of such medical events include allergic bronchospasm requiring intensive treatment in an emergency room or at home; convulsions that do not result in inpatient hospitalization or the development of drug dependency or drug abuse.

Previously planned (prior to signing the informed consent form) surgeries should not be reported as SAEs unless the underlying medical condition has worsened during the course of the study. Preplanned hospitalizations or procedures for preexisting conditions that are already recorded in the patient's medical history at the time of study enrollment should not be considered SAEs. Hospitalization or prolongation of hospitalization without a precipitating clinical AE (for example, for the administration of study therapy or other protocol-required procedure) should not be considered SAEs. However, if the preexisting condition worsened during the course of the study, it should be reported as an SAE.

#### 8.3.3 Expected Adverse Events

An adverse event (AE) is considered "expected" if:

- For approved and marketed drugs or devices, those adverse events are described in the approved Package Insert (Label).
- For investigational new drugs or devices, those adverse events are described in the FDA Investigator's Brochure.
- In clinical research studies, information on expected adverse events is also summarized in the protocol and in the consent document. See section 9.1 for the list of expected adverse events related to the drug under study.

#### 8.3.4 Unexpected Adverse Event

An adverse event (AE) is considered "unexpected" if it is not described in the Package Insert, Investigator's Brochure, in published medical literature, in the protocol, or in the informed consent document.

### 8.4 Adverse Event Characteristics

#### 8.4.1 CTCAE Term

(AE description) and grade: The descriptions and grading scales found in the NCI Common Terminology Criteria for Adverse Events (CTCAE) version 4.0 will be utilized for AE reporting. All appropriate treatment areas should have access to a copy of the CTCAE version 4.0. A copy of the CTCAE version 4.0 can be downloaded from the CTEP web site. (<http://ctep.cancer.gov>)

#### 8.4.2 Attribution of the AE

The investigator or co-investigator is responsible for assignment of attribution.

Definite – The AE is *clearly related* to the study treatment.

Probable – The AE is *likely related* to the study treatment.

Possible – The AE *may be related* to the study treatment.

Unlikely – The AE is *doubtfully related* to the study treatment.

Unrelated – The AE is *clearly NOT related* to the study treatment.

## 8.5 Serious Adverse Event Reporting Guidelines

The Sponsor Investigator will report SAEs to regulatory bodies and to the participating sites in the following manner:

### Sponsor SAE Reporting

Event occurring from Day 0 to 30 Days post last AAT infusion	Report to:		Event occurring after 30 Days post last AAT infusion	Report to:	
	FDA / IRB	Consortium		FDA / IRB	Consortium
All SAEs; ✓ Expected or Unexpected ✓ Possible, Probable, or Definite	3 Days from knowledge	Monthly	SAEs – ✓ Expected ✓ Probable or Definite OR ✓ Unexpected ✓ Possible, Probable or Definite	3 Days from knowledge	Monthly
			SAEs – ✓ Expected ✓ Possible	Annually	Monthly

- 8.5.2 The Principal Investigator must be notified within 3 business day of study team's knowledge of any event meeting the criteria and definition of a serious adverse event, regardless of attribution, occurring during the study or within 30 days of the last administration of the AAT. Kamada should be notified within 3 days to enable reporting to regulatory authorities as required.
- 8.5.3 The investigator must report all events meeting the criteria and definition of a serious adverse event that are unexpected and possibly related (definite, probable or possible to study treatment administration) to the local IRB as per local IRB policy.
- 8.5.4 All Serious Adverse Events whether expected or unexpected and possibly related (definite, probable or possible) to study treatment administration will be reported using the Serious Adverse Event form within 3 days of first awareness of the event to the MAGIC Data Coordinating Center. A copy of the form should be sent to the MAGIC Coordinator via email to [[contact]](mailto:[contact]).

The MAGIC Data Coordinating Center will disseminate information regarding serious adverse events to the participating sites within 3 days of review of the information by [name] only in the case that the event(s) is believed to be related (i.e. probably or definitely) to the study medication. All other Serious Adverse Events will be discussed on monthly webinars held with all participating centers (see section 12).

The Principal Investigator will be responsible for reporting of events to the FDA and supporters, as appropriate and defined in the regulations under 21 CFR 312.32.

## 8.6 Reporting of Unanticipated Problems

Upon becoming aware of any incident, experience, or outcome (not related to an adverse event) that may represent an unanticipated problem involving risks to subjects or others, the investigator should assess whether the incident, experience, or outcome represents an unanticipated problem. The incident, experience or outcomes are considered unanticipated if it meets all of the following criteria:

1. Unexpected (not previously documented in terms of nature, severity, or frequency);
2. Causally related or possibly related to participation in the study; and
3. Suggests that the research places subjects or others at a greater risk of harm than was previously known or recognized.

If the investigator determines that the incident, experience, or outcome represents an unanticipated problem, the investigator must report it to the MAGIC Data Coordinating Center within 3 days of first awareness of the events, and to the local IRB as per local IRB policy.

## 8.7 Stopping Rules

Although alpha-1-antitrypsin is generally safe, its use as a pre-emptive therapy for acute GVHD has not been previously studied. We will continuously monitor the incidence of BMT CTN grade 3 infections occurring within 8 weeks of study administration and accrual will be halted if there is sufficient evidence that the infection rate exceeds the acceptable target rate of 24% (the incidence in patients with high risk GVHD) by more than 30%. If the incidence of BMT CTN grade 3 infections occurring within 8 weeks of study administration is greater than the associated boundary value  $b_k$  listed in the table below, among the  $k$  patients enrolled in the trial, then accrual will be halted for safety considerations.

Maximum # of Patients, $k$	6	7-12	13-18	19-24	25-30
Boundary, $b_k$	3	5	7	9	11

Specifically, if more than 3 out of the first 6 patients, 5 out of the first 12 patients, 7 out of the first 18 patients, 9 out of the first 24 patients, or 11 out of the first 30 patients, experience grade 3 infections occurring within 8 weeks of study administration, the trial will be halted for safety considerations.

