### **5.9 Patient Replacement**

Patients who enroll in the study but do not receive any study treatment will be replaced. Patients who initiate study treatment but miss more than two doses due to non-compliance will also be replaced. The number of patients and reason(s) for replacement will be recorded and will be used to assess the feasibility of the study design.

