## 7.3 **Safety/Tolerability**

Analyses will be performed for all patients having received at least one dose of study drug. The study will use the CTCAE version 4.0 for reporting of adverse events (<http://ctep.cancer.gov/reporting/ctc.html>).

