**The operating characteristics of this stopping rule are as follows:**

	True Toxicity Rate				
	24%	30%	40%	50%	54%
Probability of Early Stopping	0.09	0.25	0.61	0.89	0.94

Using these boundaries, if the true toxicity rate is 24%, 30%, 40%, 50% or 54%, the probability of stopping the trial early is 0.09, 0.25, 0.61, 0.89, and 0.94 respectively. This stopping rule was computed using the toxbdry function in R and calculations of this function are based on methods described in Chapter 12 of Jennison and Turnbull (2000) and in the illustrative paper by Ivanova, Qaqish and Schell.

An enrollment rule to prevent an excessive number of toxicities as described in Song and Ivanova will be used to inform us of the number of additional patients we can recruit when the current patient has not yet completed cycle 1. Formally, the trial can enroll  $m$  new patients such that  $r + x + m \leq b_{n+m}$ ,  $r + x + m - 1 < b_{n+m-1}$ , and  $n + m \leq K$  where  $r$  is defined as the number of patients that have not completed follow-up and are still being followed for toxicity;  $x$  is the number of patients that have experienced toxicity and  $n$  is the total number of patients enrolled to date. This enrollment rule is conservative in that it assumes the worst case scenario, that every patient in the follow-up will experience a dose-limiting toxicity.

The study may also be stopped based on the recommendation of the investigators, the TCI DSMC, or at Kamada's discretion for any reason.

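### The infection stopping rule in Section 8.7 counts enrolled rather than dosed patients, so never-dosed patients loosen it, and it leaves K and replacements beyond 30 undefined

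*Combined protocol and SAP*

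**What the plan says.** Section 8.7 monitors "the incidence of BMT CTN grade 3 infections occurring within 8 weeks of study administration" against an "acceptable target rate of 24% (the incidence in patients with high risk GVHD"). Accrual halts if the count exceeds b_k "among the $k$ patients enrolled in the trial, then accrual will be halted for safety considerations". The boundaries are 3, 5, 7, 9 and 11 for k up to 6, 12, 18, 24 and 30. The table and the explanatory sentence both end at 30.

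The same section adds an enrolment rule. It admits m new patients if r + x + m ≤ b_(n+m), r + x + m − 1 < b_(n+m−1) and n + m ≤ K. Here r is the number still in follow-up, x is the number with an event, and n "is the total number of patients enrolled to date". K is given no value.

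Section 5.9 says: "Patients who enroll in the study but do not receive any study treatment will be replaced". It continues: "Patients who initiate study treatment but miss more than two doses due to non-compliance will also be replaced". Section 5.1.5 keeps the second group in the safety analysis but not in the efficacy assessment.

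Section 5.2 makes any treated patient evaluable for toxicity. Section 7.3 says: "Analyses will be performed for all patients having received at least one dose of study drug". Section 8.7 refers to none of Sections 5.1.5, 5.2, 5.9 or 7.3.

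**The concern.** A patient who never receives AAT cannot have an infection that is timed from study administration. Under the literal definition that patient still adds one to k and to n. The numerator is confined to dosed patients and the denominator is not, so the error runs only towards continuing accrual. This is the only numerical safety boundary in the plan, for a use of AAT that Section 8.7 itself describes as not previously studied.

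The second issue is what happens at 30. Non-compliant treated patients were exposed and belong in k, so they do not loosen the boundary. Their replacements, however, can bring the number dosed above 30, and the plan does not say whether those patients may enter or what boundary applies to them.

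**Working it through.** **Inputs.** From Section 8.7: b_k = 3, 5, 7, 9, 11 with a halt when the count exceeds b_k, and stated stopping probabilities of 0.09, 0.25, 0.61, 0.89 and 0.94 at true rates of 24%, 30%, 40%, 50% and 54%. The number of undosed patients is not in the documents, so the values below are assumptions.

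**Formula.** Let f_k(x) be the probability of x infections after k counted patients without a halt. Then f_k(x) = f_(k−1)(x)(1 − p_k) + f_(k−1)(x − 1)p_k. At each look the mass with x > b_k is removed, and the stopping probability is the total removed. Set p_k = p for a dosed patient and p_k = 0 for an undosed one. If a random share u is undosed, p_k = p(1 − u).

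**Step 1: reproduce the plan, then vary who is dosed.** Except in the row that adds patient 30, the looks are at 6, 12, 18 and 24.

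| True rate | 24% | 30% | 40% | 50% | 54% |
|---|---|---|---|---|---|
| Stated in Section 8.7 | 0.09 | 0.25 | 0.61 | 0.89 | 0.94 |
| All dosed | 0.094 | 0.239 | 0.599 | 0.883 | 0.942 |
| All dosed, look at 30 added | 0.103 | 0.270 | 0.670 | 0.931 | 0.971 |
| One undosed among the first six | 0.063 | 0.179 | 0.516 | 0.834 | 0.911 |
| Random 5% undosed | 0.075 | 0.195 | 0.524 | 0.830 | 0.905 |
| Random 10% undosed | 0.059 | 0.156 | 0.449 | 0.764 | 0.855 |
| Patients 25 to 27 undosed | 0.094 | 0.239 | 0.599 | 0.883 | 0.942 |

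The stated figures match the second row to about one percentage point. That row treats every counted patient as at risk and counts only stops through patient 24.

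**Step 2: check the first look by hand at 40%.** A halt at k = 6 needs at least 4 infections.
- All six dosed: 15(0.4⁴)(0.6²) + 6(0.4⁵)(0.6) + 0.4⁶ = 0.138 + 0.037 + 0.004 = 0.179.
- Five dosed: 5(0.4⁴)(0.6) + 0.4⁵ = 0.077 + 0.010 = 0.087.

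The infection proportion among dosed patients that is needed for a halt rises from 4/6 = 67% to 4/5 = 80%.

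**Step 3: one undosed patient at an average position, at 40%.** The stopping probability is 0.516, 0.530, 0.544, 0.562 or 0.599 when that patient falls in the first to fifth block of six. The mean is 2.751/5 = 0.55.

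**Step 4: the enrolment rule.** Take six dosed patients with r + x = 3 and one candidate (m = 1). With n = 6 the second condition is 3 < b_6 = 3, which fails. With one further never-dosed patient n = 7, and the conditions become 4 ≤ b_8 = 5 and 3 < b_7 = 5. Both hold, so this rule is loosened in the same way.

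**Step 5: beyond 30.** If K = 30, n + m ≤ K bars any entrant after the thirtieth counted patient. If K is larger, no b_k exists for that entrant. With 1, 3 or 5 further dosed entrants (assumed), the chance that a trial not halted at any of the five looks then passes 11 infections is 0.03, 0.10 or 0.16 at a true rate of 40%, and 0.006, 0.024 or 0.052 at 24%.

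**The case against.** **Intent.** The event definition and Sections 5.2 and 7.3 all point to a dosed denominator, and the sentence listing the boundaries speaks only of the first 6, 12 and so on patients. On that reading nothing is loosened. This is probably what was meant, but Section 8.7 says enrolled both for k and for n, and no other section overrides it.

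**Few patients may go undosed.** Under Section 4.0, patients found ineligible after consent are screen failures. Under Section 5.1, sites hold starting stock and treatment begins within 2 days of a confirmed score. This favours the one-patient scenarios over the 10% one. Section 5.9 nevertheless provides for such patients.

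**The enrolment rule adds protection.** If patients enter one at a time with none pending, the probability that entry is barred before 30 at the five true rates is 0.26, 0.48, 0.82, 0.97 and 0.99 with all dosed. With 10% undosed it is 0.19, 0.37, 0.70, 0.92 and 0.96. On those conditions it stays above the stated stopping probabilities. A reader might infer that real protection falls below what the plan advertises, and the documents do not establish that.

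**A tempting example fails.** A reader might infer that four infections in the first six treated patients would go unhalted once one undosed patient moves k to 7. If all four are among the first five dosed, the rule halts at k = 6. Otherwise, at n = 6 a single further patient enters only if r + x ≤ 2, which caps the first six treated at three infections. The example needs two patients admitted together.

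**Other controls.** The investigators, the oversight committee or the supplier may stop the study at any time. That discretion does not define the numerical boundary.

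**Conclusion.** The point holds as a moderate correction, not a must-fix. Read literally, Section 8.7 counts patients who are not at risk, and its stated operating characteristics then apply only if every counted patient is dosed. At a 40% true rate, one undosed patient costs about 0.05 on average (0.60 to 0.55) and about 0.08 if among the first six (0.60 to 0.52). An assumed 10% undosed costs about 0.15 (0.60 to 0.45). These are boundary-only figures that leave out the enrolment rule, and undosed patients after the twenty-fourth do not change them.

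Two stronger readings are not supported. Taking 0.67 as the 40% starting point adds the look at patient 30 and does not match the stated 0.61, so losses measured from it are not losses against the plan's own figure. It is also tempting to say that Sections 5.9 and 8.7 cannot both be followed. That is so only if K = 30, which is never stated. What the text supports is that replacements past 30 are either barred or without a boundary, depending on K.

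**What to change.** In Section 8.7, define k, n, r and x on patients who have received at least one dose of AAT, the population of Sections 5.2 and 7.3. Say that never-dosed patients do not enter these counts and that replaced non-compliant patients stay in them. With that wording, replacing never-dosed patients no longer uses up the table.

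State K and reconcile it with Section 5.9. If K is 30 dosed patients, say what happens to replacements due after the thirtieth. If K exceeds 30, recompute the whole boundary table to K with the same method, since a longer horizon may alter the existing b_k, and restate the operating characteristics with the looks they include.

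The cost is protocol wording and, if K exceeds 30, one rerun of the boundary program. Accrual may halt earlier than under the enrolled count. No patients are needed beyond the replacements already foreseen.

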**The operating characteristics of this stopping rule are as follows:**

	True Toxicity Rate				
	24%	30%	40%	50%	54%
Probability of Early Stopping	0.09	0.25	0.61	0.89	0.94

Using these boundaries, if the true toxicity rate is 24%, 30%, 40%, 50% or 54%, the probability of stopping the trial early is 0.09, 0.25, 0.61, 0.89, and 0.94 respectively. This stopping rule was computed using the toxbdry function in R and calculations of this function are based on methods described in Chapter 12 of Jennison and Turnbull (2000) and in the illustrative paper by Ivanova, Qaqish and Schell.

An enrollment rule to prevent an excessive number of toxicities as described in Song and Ivanova will be used to inform us of the number of additional patients we can recruit when the current patient has not yet completed cycle 1. Formally, the trial can enroll  $m$  new patients such that  $r + x + m \leq b_{n+m}$ ,  $r + x + m - 1 < b_{n+m-1}$ , and  $n + m \leq K$  where  $r$  is defined as the number of patients that have not completed follow-up and are still being followed for toxicity;  $x$  is the number of patients that have experienced toxicity and  $n$  is the total number of patients enrolled to date. This enrollment rule is conservative in that it assumes the worst case scenario, that every patient in the follow-up will experience a dose-limiting toxicity.

The study may also be stopped based on the recommendation of the investigators, the TCI DSMC, or at Kamada's discretion for any reason.

## 9.0 DRUG INFORMATION

### 9.1 ALPHA-1-ANTITRYPsin (AAT, AAT, A1PI)

- Commercial names for the drug: GLASSIA®
- Classification - type of agent: Human Alpha-1 Proteinase Inhibitor
- Description: AAT (Glassia) is supplied as contains a single use vial containing approximately 1 gram of functional Alpha1-PI in 50 mL of solution and a sterile filter needle
- Mode of action: The mode of action of AAT in graft-versus-host disease is not well understood, but appears to be related to its anti-inflammatory, anti-apoptotic and immunomodulatory properties.
- Pharmacokinetics: A prospective, open-label, uncontrolled multicenter pharmacokinetic trial was conducted in 7 females and 11 males with congenital Alpha-1 antitrypsin deficiency, ranging in age from 40 to 69 years. Subjects received a single dose of GLASSIA either 30 mg/kg, 60 mg/kg or 120 mg/kg. Blood samples for pharmacokinetic study were taken prior to and within 5 minutes of completion of the infusion, and then at 1 hour, 6 hours, 12 hours, 24 hours, 3 days and 7 days. The mean results for pharmacokinetic parameters in the 60 mg/kg dosage group are shown in the Table. The pharmacokinetics of GLASSIA were linear over the dose range of 30-120 mg/kg.

Pharmacokinetic Parameter	60 mg/kg Dose Group
Terminal Half-Life (h) *	111 ± 33
Area under the curve 0-168 hrs (mg·h·mL)	89 ± 10
Clearance (mL/h/kg)	0.68 ± 0.1
Volume of Distribution (L)	3.2 ± 0.3

- Adverse reactions: The most common adverse reactions (>0.5% of infusions) in clinical trials were headache and upper respiratory infection.

GLASSIA may contain trace amounts of IgA. Patients with known antibodies to IgA, which can be present in patients with selective or severe IgA deficiency, have a greater risk of developing severe hypersensitivity and anaphylactic reactions.

Because this product is made from human plasma, it may carry a risk of transmitting

infectious agents, such as viruses, the variant Creutzfeldt-Jakob disease (vCJD) and theoretically, the Creutzfeldt-Jakob disease (CJD) agent. This also applies to unknown or emerging viruses and other pathogens. The risk of transmitting an infectious agent has been minimized by screening plasma donors for prior exposure to certain viruses, by testing for the presence of certain current virus infections and by inactivating and removing certain viruses during the manufacturing process. Despite these measures, such products may still potentially transmit human pathogenic agents.

- Drug Interactions: Alpha-1-antitrypsin may interact with immunosuppressant agents and increase the risk of infection.
- Storage and stability: GLASSIA must be refrigerated between 2°C to 8°C (36°F to 46°F). Do not freeze. Product may be stored at room temperatures not exceeding 25°C (77°F) for up to one month. Once removed from refrigeration use within one month.
- Preparation:
  1. Use aseptic technique.
  2. Allow the product to reach room temperature prior to infusing and administer within three hours of entering the vials.
  3. Inspect the vial of GLASSIA. The solution should be clear and colorless to yellow-green and may contain a few protein particles. Do not use if the product is cloudy.
  4. The product is suitable for infusion directly from the vial or pooled into a sterile container for intravenous infusion.
  5. For pooling the product, use a vented spike (not supplied) to withdraw the solution from the vial and then use the supplied 5 micron filter needle to transfer the solution into the intravenous infusion container. NOTE: Do not use the 5 micron filter needle to withdraw GLASSIA from the vial.
- Administration:

For intravenous infusion only.

GLASSIA should be administered by a healthcare professional or self-administered by the patient/caregiver after appropriate training. For self-administration, provide the patient/caregiver with detailed instructions and adequate training for infusion in the home or other appropriate setting.

  1. Use aseptic technique.
  2. Inspect parenteral products visually for particulate matter and discoloration prior to administration whenever solution and container permit.
  3. Administer GLASSIA alone. Do not mix with other agents or diluting solutions.
  4. When infusing directly from the vials, use a vented spike (not supplied). If the contents of vials have been pooled to a sterile intravenous container, use an appropriate intravenous administration set.
  5. Always use a 5 micron in-line filter (not supplied) during infusion.
  6. Administer GLASSIA within three hours of entering the vials to avoid the potential ill effect of any inadvertent microbial contamination.
  7. Administer GLASSIA at room temperature through an appropriate intravenous administration set at a rate not to exceed 0.2 mL/kg body weight per minute, and as determined by the response and comfort of the patient.
  8. The recommended dosage of 90 mg/kg at a rate of 0.2 mL/kg/min will take approximately 22 minutes to infuse and dosage of 45 mg/kg will take 11 minutes to infuse.

9. Monitor the infusion rate closely during administration and observe the patient for signs of infusion related reactions. If infusion related adverse reactions occur, reduce the rate or interrupt the infusion as appropriate until the symptoms subside. Resume the infusion at a rate tolerated by the patient, except in the case of severe reaction
10. Monitor the patient for 30 minutes after completion of infusion for any adverse reactions.
11. Following administration, discard all open vials, unused solution and administration equipment.

- Availability: Provided by Kamada, Ltd.
- Return and Retention of Study Drug:  
Any remaining/expired/used is to be destroyed on site according to the institution standard operating procedure for drug destruction and documented on the drug accountability logs.
- Drug Accountability:  
The principal investigator, or a responsible party designated by the investigator, must maintain a careful record of the inventory and disposition of the investigational drug, alpha-1-antitrypsin. The drug accountability records will capture drug receipt, drug dispensing, drug return, and final disposition.

